7.5.2.3. All Days Analysis (Only CAE-free Days)

This analysis will be performed by the data analytics group. Additional details may be specified in a separate report. One possible analysis is presented below:

For each patient, all study days where the patient was CAE free will be the unit of this analysis. There are various ways to summarize albuterol use on this, for example by looking at:

- daily number of inhalations:
- albuterol use exceeding 4 inhalations (Yes/No)
- albuterol use exceeding 12 inhalations (Yes/No)

Exploratory analyses using all these patient days can be performed to predict occurrence of CAE event in the next day (for example, using logistic regression). Exploratory predictive analyses will be reported separately.

7.5.2.4. Summary Descriptive Statistics of Initial and Recurrent Clinical Asthma Exacerbation Rates

Proportion of patients with at least 1 CAE and proportion of patients with recurrent events will be presented.

7.5.3. Predicting Severe CAE/Moderate CAE from Multiple Device-Use-Measures

Predictive analysis will be performed by the data analytics group. Additional details may be specified in a separate report. Exploratory predictive analyses will be reported separately.

8. SENSITIVITY ANALYSIS

There will be no sensitivity analysis performed in this study.

9. MULTIPLE COMPARISONS AND MULTIPLICITY

No adjustment for multiplicity will be applied.

10. SAFETY ANALYSIS

10.1. General

The ITT analysis set will be used for all safety analyses.

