7.1.2. Recording and Reporting of Adverse Events

For recording of adverse event, the study period is defined for each patient as the time period from signature of the ICF to the end of visit 5 (Table 1). The period for reporting treatment-emergent adverse events is defined as the period after the 1st dose of IMP is administered and until end of visit 5.

All adverse events that occur during the defined study period must be recorded both on the source documentation and the CRF, regardless of the severity of the event or judged relationship to the test IMP. For serious adverse events, the serious adverse event form must be completed, and the serious adverse event must be reported immediately (Section 7.1.5.3.1). The investigator does not need to actively monitor patients for adverse events after the defined period.

At each contact with the patient, the investigator or designee must question the patient about adverse events by asking an open-ended question such as "Have you had any unusual symptoms or medical problems since the last visit? If yes, please describe." All reported or observed signs and symptoms will be recorded individually, except when considered manifestations of a medical condition or disease state. A precise diagnosis will be recorded whenever possible. When such a diagnosis is made, all related signs, symptoms, and any test findings will be recorded collectively as a single diagnosis on the CRF and, if it is a serious adverse event, on the serious adverse event form.

The clinical course of each adverse event will be monitored at suitable intervals until resolved, stabilized, or returned to baseline; or until the patient is referred for continued care to a healthcare professional; or until a determination of a cause unrelated to the test IMP or study procedure is made.

The onset and end dates, duration (in case of adverse event duration of less than 24 hours), action taken regarding IMP, treatment administered, and outcome for each adverse event must be recorded both on the source documentation and the CRF.

The relationship of each adverse event to test IMP and study procedures and the severity and seriousness of each adverse event, as judged by the investigator, must be recorded as described below.

Further details are given in the Safety Monitoring Plan.

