9.2.3. Safety Analysis Set

The safety analysis set will include all enrolled patients who receive at least 1 dose of the test IMP. In this analysis population, treatment will be assigned based on the treatment patients actually received unless otherwise specified. This analysis population will be used for analysis and summarization of safety data.

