9.7. Safety Analysis

Safety analyses will be performed on the safety analysis set (Section 9.2.3).

Safety assessments and time points are provided in Table 1.

All adverse events will be coded using the Medical Dictionary for Regulatory Activities. Each patient will be counted only once in each preferred term or System Organ Class category for the analyses of safety. Summaries will be presented for all adverse events (overall and by severity), adverse events determined by the investigator to be related to test IMP (ie, reasonable possibility [Section 7.1.4], defined as related or with missing relationship; overall and by severity), serious adverse events, and adverse events leading to withdrawal from the study. Patient listings of serious adverse events and adverse events leading to withdrawal will be presented.

The use of concomitant medications will be summarized by therapeutic class using descriptive statistics.

For continuous variables, descriptive statistics (number, mean, standard deviation, median, minimum, and maximum) will be provided for actual values and changes from baseline to each time point. For categorical variables, patient counts and percentages will be provided. Descriptive summaries of serious adverse events, patient withdrawals due to adverse events, and potentially clinically significant abnormal values (physical examination) based on predefined criteria will be provided as well.

If any patient dies during the study, a listing of deaths will be provided, and all relevant information will be discussed in the patient narrative included in the CSR.

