3. ANALYSIS SETS

3.1. Intent to Treat Analysis Set

The intent-to-treat (ITT) analysis set will include all enrolled patients regardless of whether a patient took any investigational medicinal product (IMP). A patient is considered enrolled according to the status reported in the database. This analysis set will be used for endpoint analysis and safety analysis.

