3.3. Safety Analysis Set

The safety analysis set will include all enrolled patients who receive at least 1 dose of the IMP.

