10.4. Adverse Events

All treatment emergent adverse events will be coded using the MedDRA. Adverse events will be included as treatment emergent based on the date of the baseline (ie, the earliest date an ABS eMDPI device was dispensed). Each patient will be counted only once in each PT Term or SOC category for the analyses of safety. Summaries will be presented for all adverse events (overall and by severity), adverse events determined by the investigator to be related to test IMP (ie, reasonable possibility [Table 5 in Section 7.1.4 of the protocol], defined as related or with missing relationship; overall and by severity), serious adverse events, CAE related adverse events, and adverse events leading to withdrawal from the study, asthma exacerbations by severity, and asthma exacerbations by deterioration.

Patient listings for all adverse events, of serious adverse events and adverse events leading to withdrawal will be presented.

If any patient dies during the study, a listing of deaths will be provided, and all relevant information will be discussed in the patient narrative included in the CSR.

Any adverse event or serious adverse event with a missing start date will be considered treatment emergent.

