20.2. Modified Intent-To-Treat Analysis Set

Statistical Analysis Plan Section	Protocol Section	Protocol Description	Statistical Analysis Plan Change	Rationale
3.2	9.2.2	The modified intent-to-treat (mITT) analysis set is a subset of the ITT analysis set that will include only the patients who used the IMP at any time during the study. This analysis population will be used for endpoint analysis”.	The modified intent-to-treat (mITT) analysis set is a subset of the ITT analysis set that will include patients who used the IMP at any time during the study and patients who did not use the IMP at any time during the study provided these patients complied with study requirements and the ABS eMDPI inhalers were available for data download at the end of the study.	This study is to evaluate the relationship between as-needed usage of ABS eMDPI and CAE/severe CAE. As-needed usage may include no usage if patients’ health did not require ABS eMDPI use. Endpoint analyses will be summarized using the ITT analysis set.

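### Adverse events are tabulated in all enrolled patients from dispensing, so no planned table gives incidence in dosed patients after dosing; the size of the difference is unknown and probably small

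*SAP*

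**What the plan says.** **Population.** SAP 10.1: "The ITT analysis set will be used for all safety analyses". SAP 3.1 defines ITT as every enrolled patient, dosed or not. SAP 3.3 still carries a narrower set, "The safety analysis set will include all enrolled patients who receive at least 1 dose of the IMP", but no section of the SAP assigns an analysis to it. Of that same set, protocol 9.2.3 says "This analysis population will be used for analysis and summarization of safety data", and protocol 9.7 repeats the assignment.

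**Start of treatment-emergence.** SAP 10.4: "Adverse events will be included as treatment emergent based on the date of the baseline", where baseline is the earliest date a device was dispensed. Events with a missing start date also count. Protocol 7.1.2 has the treatment-emergent period "defined as the period after the 1st dose of IMP is administered and until end of visit 5".

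**Non-use.** SAP 20.2 allows that "As-needed usage may include no usage" where a patient's health did not call for the inhaler. SAP 5.2 includes a disposition count of enrolled patients with no use.

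**What is declared.** SAP 20.1 and 20.3 record the move of safety to ITT. The amendment history attributes it only to a study-team decision. None of the four entries in Section 20 covers the start of treatment-emergence. The amendment history describes the 10.4 edit as a clarification.

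**The concern.** A stated objective of the study is to evaluate safety in use of this inhaler. For an as-needed product, being enrolled and handed a device is not the same as having taken a dose. The first inhalation may come after the dispensing date, or not at all.

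The SAP's denominator can therefore include people with no exposure, and its numerator can include events that precede any exposure. Because each patient is counted once per term and exposure time is not in the denominator, nothing later in the analysis corrects for this. No planned table shows incidence in dosed patients, which is the quantity the protocol set out to report. A reader comparing these percentages with earlier experience of the product would be comparing different quantities.

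**Working it through.** **The plan's own figures.** The only relevant number is the planned size. SAP 2.3 has 360 evaluable patients and 10% dropout: 360 / (1 - 0.10) = 400 enrolled, which reproduces. The documents give no expected adverse event rate, no never-dosed share and no time to first use. Everything below rests on assumed values and shows only how the two definitions can differ.

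**Notation**
- u: share of enrolled patients who never dose.
- p: incidence after first dose in dosed patients, which is the protocol's quantity.
- q: extra share of dosed patients whose only event falls between dispensing and first dose.
- r: incidence after dispensing in never-dosed patients.

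**Formula.** SAP rate = (1 - u)(p + q) + u × r. The protocol rate is p.

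**Assumed p = 10%, N = 400.** Cells are the rate the SAP would report.

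| u | never dosed | q = 0, r = 0 | q = 0, r = p | q = 3%, r = 0 | q = 3%, r = p |
|---|---|---|---|---|---|
| 0% | 0 | 10.00% | 10.00% | 13.00% | 13.00% |
| 2% | 8 | 9.80% | 10.00% | 12.74% | 12.94% |
| 5% | 20 | 9.50% | 10.00% | 12.35% | 12.85% |
| 10% | 40 | 9.00% | 10.00% | 11.70% | 12.70% |
| 20% | 80 | 8.00% | 10.00% | 10.40% | 12.40% |

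One cell in full (u = 5%, q = 3%, r = 0): 0.95 × (0.10 + 0.03) + 0.05 × 0 = 12.35%.

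**Assumed p = 30%.** With u = 20%, q = 0 and r = 0 the SAP rate is 0.80 × 30% = 24.00%. With u = 0 and q = 3% it is 33.00%.

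**Reading the results**
- Over these ranges the ratio of SAP rate to protocol rate runs from 0.80 (8.00/10.00, or 24.00/30.00) to 1.30 (13.00/10.00). It can fall on either side of 1.
- Since q and r cannot be negative, the SAP rate cannot fall below (1 - u)p. It reaches that floor only with no pre-dose events and no events among never-users.
- The two rates are equal if every patient doses and no event precedes dosing (u = 0, q = 0). They are also equal if q = 0 and never-users have the same incidence as users (r = p).

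**The case against.** The case for leaving the SAP as it is has real content.

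- **The population change is open.** It is in the amendment history and in SAP 20.1 and 20.3, and the SAP's introduction says that the SAP prevails over the protocol. A reader might infer a concealed departure; the documents do not support that. What stands is that no substantive reason is given. For treatment-emergence, the introduction also allows a difference to be explained in the CSR, so its absence from Section 20 is a gap but not yet a breach.
- **Never-users may be few or none.** Entry requires an ACQ-5 of at least 1.5 and a severe exacerbation in the past year, and this inhaler replaces all other rescue treatment. A reader might take SAP 20.2 to say that some patients will never use it, but the text states a possibility with a condition attached. Patients must also show competent use before receiving devices (protocol 3.1). The documents do not say whether that involves inhaling drug, and SAP 5.2 still provides a count of non-users.
- **Dilution is not established.** It is tempting to conclude that rates are understated. Common events listed in protocol 1.2.2.1, such as upper respiratory infection and headache, need no inhalation to occur, and pre-dose events push the rate up.
- **Time before first use is not counted as exposure.** A reader might infer this from the dispensing-based start. SAP 10.2 counts only days with an inhalation, and adverse events are counted by patient, so no planned analysis contains that error.
- **Dispensing is a robust start date.** It does not depend on a successful download, and it misses no post-dose event. This argues for a fallback rule and for keeping the ITT table, but not for having it as the only table.
- **A reader can partly bound the effect.** Non-users are counted, exposure is summarised and all adverse events are listed by patient. That falls short of a table in dosed patients.

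**Conclusion.** The point holds in a limited form. The planned percentages are incidences among enrolled patients after dispensing. The protocol called for incidences among dosed patients after dosing, and the SAP keeps the set needed for that without using it. The population change is declared without a substantive reason; the treatment-emergence change is not reconciled in Section 20.

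Size and direction cannot be derived, because u, q and r are not in the documents. Under the assumed ranges (u from 0 to 20%, q of 0 or 3%, r from 0 to p, p of 10% or 30%) the SAP rate is 0.80 to 1.30 times the protocol rate. These ranges are illustrative, and the true effect is probably small in a population this symptomatic. Safety is descriptive and single-arm, so no test or error rate is affected. The change is still worth making, because it answers the stated safety objective directly and needs no new data.

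**What to change.** 1. Present the adverse event tables on the safety analysis set of SAP 3.3, counting events with onset on or after the first recorded inhalation.
2. Add a fallback. Where device data could not be downloaded and non-use cannot be confirmed, treat the patient as dosed and use the dispensing date as the start.
3. List separately the events that precede the first dose and the events in never-dosed patients.
4. Keep the ITT-from-dispensing table as supporting.
5. Enter the treatment-emergence change in SAP Section 20, and add a reason for the population change in 20.1 and 20.3.

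The cost is one extra set of tables, the fallback rule and an SAP amendment. The inhalations are already time-stamped by the device, so nothing more has to be collected. SAP 2.4.2 requires amendments to be approved before database lock. After that point, protocol Section 9 allows added analyses that are disclosed and justified in the CSR.

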10.2. Duration of Exposure to IMP

Duration of exposure to IMP (days and weeks) for the individual patient is the number of days the patient took at least 1 inhalation from the ABS eMDPI. Patients receive the ABS eMDPI devices at Baseline and subsequently by courier on Day 21. Duration of exposure is determined from all eMDPIs used by a patient and it is the total number of unique dates recorded by the eMDPIs from the dispense date and return date of a given device, inclusive. Note, if a patient uses more than 1 eMDPI device on a given day, it is still only 1 day of exposure for that given day. The patient's last date of contact or study completion date will be used as the device return date if the device return date is missing.

Duration of exposure (days and weeks) will be summarized using descriptive statistics overall, and by CAE status and by CAE severity.

Exposure to IMP, expressed in mcg units, will also be summarized using descriptive statistics. Average daily exposure, average weekly exposure, and the maximum exposure in a single day will be summarized overall, and by CAE status and CAE severity. One inhalation recorded by the ABS eMDPI is equivalent to 90 mcg.

10.3. Time on Study

Duration of time on study (days and weeks) will be summarized using descriptive statistics overall, and by CAE status and by CAE severity.

10.4. Adverse Events

All treatment emergent adverse events will be coded using the MedDRA. Adverse events will be included as treatment emergent based on the date of the baseline (ie, the earliest date an ABS eMDPI device was dispensed). Each patient will be counted only once in each PT Term or SOC category for the analyses of safety. Summaries will be presented for all adverse events (overall and by severity), adverse events determined by the investigator to be related to test IMP (ie, reasonable possibility [Table 5 in Section 7.1.4 of the protocol], defined as related or with missing relationship; overall and by severity), serious adverse events, CAE related adverse events, and adverse events leading to withdrawal from the study, asthma exacerbations by severity, and asthma exacerbations by deterioration.

Patient listings for all adverse events, of serious adverse events and adverse events leading to withdrawal will be presented.

If any patient dies during the study, a listing of deaths will be provided, and all relevant information will be discussed in the patient narrative included in the CSR.

Any adverse event or serious adverse event with a missing start date will be considered treatment emergent.

10.5. Deaths

A listing of deaths by patient and narratives will be provided, if any patient dies during the study.

10.6. Clinical Laboratory Tests

Any patient who experiences menarche following screening will be required to have a negative urine pregnancy test prior to dosing with IMP. If a patient has a positive urine pregnancy test, then she will be discontinued from the study. A urine pregnancy test for women of childbearing potential will be performed at the Screening and Final/Early Termination visit.

A listing of urine pregnancy test by patient will be provided.

10.7. Physical Examinations

Physical examinations will be performed at screening and exacerbation visits.

A physical examination that includes, at a minimum, skin, lungs, cardiovascular, respiratory, gastrointestinal, and neurological assessments are completed at the Screening visit (eg, baseline values] and exacerbation visits. Height (to be obtained at the Screening visit only) and weight will also be measured and recorded. Any pre-existing abnormality will be reported as a part of medical history and any ongoing abnormality identified at Screening and any new findings or clinically significant change (worsening) identified at an exacerbation visit will be reported as an adverse event.

10.8. Concomitant Medications or Therapies

Concomitant therapies and medications, including medications that are taken on an as needed basis and occasional therapies, will be monitored during the study. Details of prohibited medications may be found in Section 5.6 of the study protocol. All concomitant medications will be coded using the WHO Drug Dictionary.

The incidence of concomitant therapies and medications will be summarized using descriptive statistics by therapeutic class category and PT. Patients are counted only once in each therapeutic class, and only once in each PT category. Concomitant therapies and medications for a given patient will include all medications up to the end of the patient's participation in the study (date of completion, withdrawal, lost to follow-up, or death).

A listing of all concomitant therapies and medications by patient and the study day the therapy or medication was started will be provided.

11. TOLERABILITY VARIABLES AND ANALYSIS

Tolerability was not specifically defined for this study.

12. PHARMACOKINETIC ANALYSIS

Not applicable.

13. PHARMACODYNAMIC ANALYSIS

Not applicable.

14. PHARMACOKINETIC/PHARMACODYNAMIC ANALYSIS

Not applicable.

15. BIOMARKER ANALYSIS

Not applicable.

16. IMMUNOGENICITY ANALYSIS

Not applicable.

17. ANCILLARY STUDIES ANALYSIS

Not applicable.

18. PLANNED INTERIM ANALYSIS

Not applicable.

19. STATISTICAL SOFTWARE

All data listings, summaries, and statistical analyses will be generated using SAS[®] version 9.1.3 or higher.

20. CHANGES TO ANALYSES SPECIFIED IN THE STUDY PROTOCOL

20.1. Intent-To-Treat Analysis Set

Statistical Analysis Plan Section	Protocol Section	Protocol Description	Statistical Analysis Plan Change	Rationale
3.1	9.2.1	The intent-to-treat (ITT) analysis set will include all enrolled patients regardless of whether or not a patient took any IMP. A patient is considered enrolled according to the status reported in the database. This analysis population will be used for summarization of patient disposition.	The intent-to-treat (ITT) analysis set will include all enrolled patients regardless of whether a patient took any investigational medicinal product (IMP). A patient is considered enrolled according to the status reported in the database. This analysis set will be used for endpoint analysis and safety analysis.	Patient disposition will be summarized using all patients entered into the database not just enrolled patients, since all patients are needed to descriptively summarize patients screened, patients screened but not enrolled and reason for non-enrollment. All endpoint and safety analyses will use the ITT analysis set.

20.2. Modified Intent-To-Treat Analysis Set

Statistical Analysis Plan Section	Protocol Section	Protocol Description	Statistical Analysis Plan Change	Rationale
3.2	9.2.2	The modified intent-to-treat (mITT) analysis set is a subset of the ITT analysis set that will include only the patients who used the IMP at any time during the study. This analysis population will be used for endpoint analysis”.	The modified intent-to-treat (mITT) analysis set is a subset of the ITT analysis set that will include patients who used the IMP at any time during the study and patients who did not use the IMP at any time during the study provided these patients complied with study requirements and the ABS eMDPI inhalers were available for data download at the end of the study.	This study is to evaluate the relationship between as-needed usage of ABS eMDPI and CAE/severe CAE. As-needed usage may include no usage if patients’ health did not require ABS eMDPI use. Endpoint analyses will be summarized using the ITT analysis set.

